IRB Study Number: 20210068 Date: August 24, 2023

Protocol Title:	Adherence to Electrical Glossal In Situ Stimulation for Sleep Apnea
Protocol Number	20210068
Protocol Version:	2.0
NCT Identifier	NCT04974515
PI Name:	[name]. MD.
Target Population:	Mild Obstructive Sleep Apnea (OSA)
Study/Trial Design:	Prospective randomized parallel-group trial comparing high versus low intensity eXciteOSA device
Primary Objective:	To assess whether adherence to the eXciteOSA® device varies as a function of level of stimulation in patient with mild OSA.
Secondary Objectives:	To assess whether the level of adherence to the eXciteOSA® is associated with improvements in respiratory event index (REI), daytime sleepiness as assessed with the Epworth Sleepiness Scale, snoring intensity as assessed by bed partner reports using a visual analog scale, and quality of life.
Endpoints	 Primary: Adherence to the eXciteOSA® device defined as the number of days device used and the number of sessions over the 6-week period. Secondary. Respiratory event index (REI) Epworth Sleepiness Scale (ESS) score Snoring visual analog scored assessed by partner SF-20 EQ-5D-5L Pittsburgh Sleep Quality Index (PSQI) Work Productivity and Activity Impairment Questionnaire Acceptance of long-term treatment
Sample Size:	40 (20 per arm)

Date: August 24, 2023

1. Protocol Title

Adherence to Electrical Glossal In Situ Stimulation for Sleep Apnea (The AEGIS study)

2. IRB Review History*

Not applicable

3. Objectives*

Aim 1: To assess whether adherence to the eXciteOSA® device varies as a function of level of stimulation in patients with mild OSA.

Aim 2: To assess whether the level of adherence to the eXciteOA® is associated with improvements in respiratory event index (REI), daytime sleepiness as assessed with the Epworth Sleepiness Scale, snoring intensity as assessed by bed partner reports using a visual analog scale, and quality of life.

4. Background*

Obstructive sleep apnea (OSA) is a common, chronic, sleep disorder characterized by recurrent collapse and obstruction of the pharyngeal airway during sleep. Untreated OSA is associated with long-term health consequences including hypertension, prevalent cardiovascular disease, type 2 diabetes, cognitive impairment, and depression. Common symptoms include excessive daytime sleepiness, fatigue, non-refreshing sleep, nocturia, morning headache, irritability, and memory loss. Untreated OSA is also associated with lost productivity and workplace and motor vehicle accidents resulting in injury and fatality. The costs of untreated OSA and sleep loss are substantial. Treatment can relieve symptoms and reduce some of the associated sequelae. However, many people with OSA struggle with the first-line therapy, positive airway pressure CPAP), for which adherence rates remain unacceptably low. Non-PAP therapies (e.g., oral appliance therapy) are beneficial in many cases but have variable and unpredictable efficacy. Thus, new approaches to treat OSA are required. The problem of adherence to PAP therapy for OSA is particularly problematic for patients with mild OSA. Although the clinical consequences of mild obstructive sleep apnea are poorly defined, patients with mild disease might present with debilitating symptoms that warrant treatment. Although alternative options, such as oral appliance therapy, are available for the management of mild sleep apnea and have comparable efficacy to PAP therapy in sleepiness and disease-specific quality of life, it is not without its drawbacks including discomfort and pain particularly with the temporomandibular join, the need for custom fitting, excessive salivation, dental misalignment, tooth movement, and gum irritation. Thus, alternative therapeutic approaches are needed to treat mild and moderate sleep apnea. The eXciteOSA® device is a possible alternative that uses electrical stimulation of the tongue during the day for one 20-minute session. The device is based on the premise that improving muscle endurance and responsiveness will lead to a decrease in collapsibility of the upper airway during sleep. In fact, studies that used other means for training the upper airway during sleep have shown that OSA severity can, in fact, be decreased. Preliminary work on the eXcite device has shown that there is improvement in snoring intensity, reduction in the AHI, and resolution of daytime sleepiness as assessed by the Epworth Sleepiness Scale. While the simplicity and potential efficacy of the eXciteOSA® device provide a promising venue for treatment of snoring, mild sleep apnea, questions remain as to the potential adherence to the use of the device. Foremost is the question of whether adherence is a function of the intensity of stimulation. Thus, the current study was designed to examine adherence levels to the eXcite device in patients with mild OSA.

Page 2 of 7 Revised: June 17, 2020

Date: August 24, 2023

Utilizing a randomized design, we will examine whether adherence differs between high vs. low intensity.

5. Inclusion and Exclusion Criteria*

Inclusion Criteria

- a) Age \geq 18 years
- b) Ability to consent
- c) In-lab or home sleep apnea test demonstrating mild obstructive sleep apnea.
- d) Smartphone or tablet that can run the eXciteOSA app

Exclusion criteria:

- a) Current pacemaker, defibrillator, or neurostimulation device
- b) No prior oropharyngeal surgery for OSA
- c) No implants, metal prostheses, dental braces, or soft tissue/bony ulcerations in the oral cavity
- d) No prior use of mandibular advancement device (MAD) or continuous positive airway pressure (CPAP)
- e) Heart failure New York Heart Association Class 3 or 4; or ejection fraction < 45%
- f) Active coronary disease defined as an intervention (e.g., angioplasty, coronary artery bypass surgery) in the prior 6 months
- g) Uncontrolled HTN BP 160/100
- h) Clinician diagnosis of any chronic lung disease except asthma
- i) Chronic fatigue syndrome or fibromyalgia
- j) Self-reported current illicit drug use in the past 30 days
- k) Self-reported use of marijuana or opiates in the past 30 days
- I) Use of supplemental oxygen
- m) Self-reported use of prescribed or over the counter sleeping medications in the past 30 days
- n) Current pregnancy or intention of becoming pregnant
- o) Oropharyngeal abnormalities (class 2 or class 3 malocclusion)
- p) Periodic breathing (Cheyne Stoke respiration)
- q) Central sleep apnea (central apnea index [CAI] < 5/h)
- r) Investigator discretion
- s) Prisoners

6. Number of Subjects*

We propose to recruit a sample size of 40 patients with mild sleep apnea for this study.

7. Study-Wide Recruitment Methods*

Recruitment for potential participants will be based on clinical and community efforts. Patients with mild sleep apnea, as determined by a home sleep apnea test or an in-lab study conducted as part of routine clinical care, will be recruited from the patient panel of the study investigators. In addition, referrals from other physicians who become aware of the study will be screened for participation. In addition, volunteers responding to study flyers or advertisements will be interviewed on the telephone by the study staff using a screening questionnaire in RedCap to assess eligibility. Subjects whose questionnaire responses meet eligibility will be scheduled for an in person or a telehealth/video visit. At the first visit, the protocol will be explained in detail and written informed consent obtained. Study flyers will be posted at: (a) U-Miami sleep clinic (b) grocery stores; and (c) community centers. In addition, we will also use social media posts to recruit for the study. There will be no effort made to otherwise review medical records to identify or recruit other patients.

Page 3 of 7 Revised: June 17, 2020

Date: August 24, 2023

8. Study Timelines*

a) Participant eligibility: Eligibility (via phone) of study participants will be assessed either by telephone, a video visit, or if needed an in-person visit. Based on whether the participant meets initial study criteria, a visit will be scheduled for informed consent before any study procedures.

- b) Screening (1-2 visits): If a participant does not have any exclusion criteria based on the preliminary screen, they will be invited for a visit to complete the consent process and assess remaining eligibility criteria before any study procedures. Assessment of remaining eligibility criteria will include: (a) urine pregnancy test in women; (b) oral exam assessment to assess for oropharyngeal abnormalities, and (c) blood pressure. Individuals who consent to participate in the study will be provided a self-applied monitor (Nox A1, Nox Medical) to record three nights of sleep in the home setting (research procedure). The Nox A1 monitor allows for an assessment of breathing abnormalities during sleep using self-applied electrodes that collect the necessary physiologic signals (e.g., oxygen saturation, respiratory effort). Analysis of the acquired physiological signals will be used to the Respiratory event index ([REI] = Number of respiratory events per hour based on a 3% desaturation threshold). Only those participants with a REI of 5.0-14.9 events/hr (i.e., mild OSA) will be considered for continued screening. We will aim to collect three nights of data using the Nox A1 and use a minimum window of 2 weeks to complete all sleep testing if any particular night attempt fails. A study with less than 3h recording time will be considered a failure and repeat attempt will be made.
- c) Baseline Assessments: Participants will complete the following baseline assessments: (a) a questionnaire packet including the ESS, the Medical Outcomes Study Short Form Survey-20 (SF-20), snoring visual analog scale (VAS) completed by the partner, EuroQOL EQ-5D-5L, Pittsburgh Sleep Quality Index (PSQI), Work Productivity and Activity Impairment Questionnaire, and global assessment survey, (b) physical exam including body mass index (BMI), anthropometry (waist and neck circumference), an upper airway assessment for Friedman and tonsillar score, oropharyngeal abnormalities, blood pressure, and (c) an assessment of prevalent medical comorbidity and current medication use. Participants will be provided with instructions on use of the eXciteOSA® device and the associated smartphone app. After the baseline assessment, participants will be randomized to either the high intensity versus low intensity stimulation arm. Within each arm, the participant will be further able to further adjust the degree of stimulation level on a range of 1-15.

Study investigators, staff, and the participants will be blinded to the treatment assignment. Allocation to a specific arm will be based using a computer/digital randomization scheme using blocks of four to keep the sizes of treatment groups similar. The assignment table will be used the manufacturer to tag the devices in the sequence of use prior to shipment. The allocation table will be shared with the investigators and all involved in the study including the patients after the study is completed.

d) Follow-up Assessments: After a 6-week period of use of the eXciteOSA® device, all of the baseline assessments will be repeated including (a) 3 nights of Nox A1 monitoring within a 2-week period), (b) a questionnaire packet as before, (c) physical exam including body mass index (BMI), anthropometry (waist and neck circumference), an upper airway assessment, blood pressure, and (d) ongoing medication use.

Date: August 24, 2023

It is anticipated that the study duration for a participant will be about 3 months. The number of study visits required are as follows:

- Consent visit (setup with 20-minute run-in period with eXcite device)
- Baseline assessments (questionnaires, BMI, neck circumference, Mallampati score, history/medication inventory) (can be completed within 1 or 2 visits).
- Follow-up assessments (after 6-weeks of use) [Can be completed within 1 or 2 visits].

Thus, we expect a up to five visits over an approximate 3 month period.

Post Study Follow-up: At the end of the study, the participant will be transitioned to a sleep clinic and physician of his / her choice. Continued therapy with the eXcite OSA device after the study period will be determined by the participant and the treating sleep physician. Therapy can continue if the primary sleep physician deems it to be clinically appropriate and the participant agrees to continue. We propose to follow-up the adherence to therapy for 12 month period.

9. Study Endpoints*

a. Primary outcome variable.

Adherence to the eXciteOSA® device defined as the number of days device used and the number of sessions over the 6-week period. The device usage data are stored in the device that can be used to assess overall use.

- b. Secondary outcome variables.
 - Respiratory event index (REI)
 - Epworth Sleepiness Scale (ESS) score
 - Snoring visual analog scored assessed by partner
 - SF-20
 - EQ-5D-5L
 - Pittsburgh Sleep Quality Index (PSQI)
 - Work Productivity and Activity Impairment Questionnaire
 - Acceptance of treatment at 6 weeks

10. Procedures Involved*

Home sleep study: Recording methods for sleep will include continuous monitoring of EEG, EOG (electrooculogram), oronasal airflow (by a pressure sensitive nasal cannula), pulse oximetry, and thoracic and abdominal movements. There are no risks related to routine monitoring of sleep. Electrode placement may lead to a minor skin reaction in rare situations that is most often self-limited.

Home treatment with eXciteOSA® device: This is an FDA approved treatment for snoring and mild obstructive sleep apnea in patient who are 18 years or older. The device works by delivering electrical muscle stimulation through a mouthpiece that sits around the tongue. The eXciteOSA mouthpiece has four electrodes, two located above the tongue and two located below the tongue. The device provides electrical muscle stimulation action in sessions that consist of a series of electrical pulses with rest periods in between. It is used for 20 minutes a day during a wakeful state.

Stimulation Level: With each arm, participants will have the ability to increase the stimulation level which has a scale of 1-15. Instructions will be provided to participants to advance the stimulation level as tolerated based on the experience from a prior session. If at any level, the participant feels that the stimulation is excessive, the participant can adjust the level down even during a session. At

Date: August 24, 2023

the highest setting of 15 in either arm, the maximum voltage (current) levels for the low and high intensity arms are 6.7 V (11.1 milliamps) and 29.8 V (58.6 milliamps), respectively. Physicians involved in the study will guide the participant on the use of varying levels of stimulation intensity as will be any study staff who are added to the investigative team.

11. Data and Specimen Banking

There are no specimens that will be banked for future use.

12. Data Management*

Statistical analyses for the primary evaluation of adherence will follow the intention-to-treat paradigm, which means that all randomized patients will be included in the treatment group to which they were assigned. Participants who do not have the requisite data for our primary outcomes will be accounted for and compared by assigned group. Participants not able to be included in the intention-to-treat analyses will be compared to those who are included with respect to demographic and other characteristics.

The primary outcome for the study is the overall adherence to the eXciteOSA® device as determined by the number of days the device was used out of 42 days (6 weeks) as instructed. Initial analyses will tabulate demographic and baseline characteristics of the participants by randomization group. χ^2 -tests and one-way ANOVA will be used to compare groups on these characteristics. If differences in some characteristics are observed, even though not statistically significant, these variables will be considered for inclusion in regression models assessing our outcomes. The analytical approach will consist of using mixed model linear regression of adherence with an indicator variable for the fixed effect for treatment group and baseline value of the measure. Additional covariates (e.g., age, sex, BMI) will be included in the model particularly if the randomization results in imbalances in a covariate across treatment groups.

The secondary outcomes include change in: (1) REI (2) ESS score, (3) snoring assessment from the bed partner using a visual analog score, (6) SF-20 and EQ-5D-5L quality of life scores; (7) PSQI score, (8) Work Productivity and Activity Impairment Questionnaire, and (8) acceptance of long-term treatment. All analyses for our secondary outcomes will be done under the intention to treat principle. Initial analyses will tabulate baseline characteristics of participants by randomization group. For our continuous outcomes, we will use multivariable regression and mixed model repeated measures analyses as done for the primary outcomes.

13. Provisions to Monitor the Data to Ensure the Safety of Subjects*

The principal investigator will have the responsibility for monitoring and oversight of any study related events or problems. No interim analysis or interpretation of data for a safety signal are included as the eXciteOSA® therapy will be used for its approved indication. Any adverse event will be notable during the visit itself and any unexpected untoward event will be reported to the IRB by the PI within 48 hours of occurrence. Performance of sleep testing and other assessments planned are all part of the routine clinical practice and the procedures for these are well established.

14. Withdrawal of Subjects*

A subject will be withdrawn from the study if he/she does not wish to complete the testing as specified by the study protocol.

Page 6 of 7 Revised: June 17, 2020

Date: August 24, 2023

15. Risks to Subjects*

Questionnaires: There are no risks to completing the study questionnaires.

Overnight sleep study: There are no major risks with a sleep study. Rarely, some individuals may experience minor redness or irritation at the site of the monitoring electrodes from the sleep study.

Anthropometry: There are no risks with anthropometric measurements.

eXciteOSA® Device: There are no major side effects of using the eXciteOSA® device. Expected minor side effects from using the eXciteOSA® device include pooling of saliva, tooth sensitivity during use and tingling of the tongue that can continue after use. All of these side effects are transient and resolve shortly after use of the device stops.

Page 7 of 7 Revised: June 17, 2020

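### Exclusion (q) is inverted as printed: it is labelled central sleep apnea but set at a central apnea index below 5/h

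*Combined protocol and SAP*

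**What the plan says.** Exclusion (q) in Section 5 reads "Central sleep apnea (central apnea index [CAI] < 5/h)". Section 8(b) shows how the list is used: a person goes on to the consent visit only if the preliminary screen finds no exclusion criterion. Meeting (q) therefore means being ruled out.

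Other places that bear on the point:

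- **Who the trial is for.** The title table gives the target population as "Mild Obstructive Sleep Apnea (OSA)". Inclusion (c) asks for "In-lab or home sleep apnea test demonstrating mild obstructive sleep apnea".
- **How the device is meant to work.** Section 4 describes the intended effect as a "decrease in collapsibility of the upper airway during sleep".
- **Neighbouring exclusions.** Item (e) uses the same sign in the disqualifying direction, "ejection fraction < 45%". Item (p) is "Periodic breathing (Cheyne Stoke respiration)", with no number. Item (r) is investigator discretion.
- **REI.** Section 8(b) defines it as respiratory events per hour at a 3% desaturation threshold and admits people with 5.0-14.9 events/h.
- **Wording of (b)-(d).** These sit in the exclusion list but are phrased as requirements to enter, for example "No prior oropharyngeal surgery for OSA" and "No implants, metal prostheses, dental braces, or soft tissue/bony ulcerations in the oral cavity".

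**The concern.** An exclusion that names a condition and then gives a number should use the number to identify people who have the condition. In (q) the number picks out people with few or no central apneas. Label and inequality point in opposite directions, so both cannot be followed.

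Two things are at stake. The first is who gets in. Item (q) is the only numeric rule on central events in a trial of an obstructive disorder, testing a device aimed at upper-airway collapse. If the printed rule were applied, people with substantial central apnea would not be stopped by it. Their REI, a secondary outcome and part of Aim 2, would include events that the device is not described as treating.

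The second is the record of eligibility. Section 7 describes a screening questionnaire in RedCap. If a form carries (q) literally, it screens in the wrong direction relative to the label. If staff follow the label instead, they depart from the written criterion. Either way, protocol and practice would disagree on an eligibility rule.

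**Working it through.** The plan gives no calculated figure here, so the check is logical: apply the printed rule, try the alternative readings, and look for anything elsewhere that corrects it.

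**Step 1. The rule as printed.** Excluded by (q) if CAI < 5/h.

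| CAI (/h) | CAI < 5? | Result under (q) |
|---|---|---|
| 0 | yes | excluded |
| 4.9 | yes | excluded |
| 5.0 | no | not excluded |
| 10 | no | not excluded |

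Combined with the REI window in Section 8(b), the only people who would pass both rules are those with REI 5.0-14.9/h and CAI of 5/h or more. That is hard to square with a mild obstructive population.

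**Step 2. Other readings.**

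- *Label and number jointly* (has central sleep apnea and has CAI < 5/h). A person with no central apneas is no longer caught. A person at 5/h or more still fails the second condition, so is still not excluded.
- *Label alone, number ignored.* The direction is then sensible, but the printed threshold does no work and no boundary is left.
- *Number as a requirement to enter*, in the style of (b)-(d). This may explain how the slip arose. But (q) carries a disease label with no negation, so it is not written in that form.

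No reading that keeps (q) as an exclusion and gives the printed inequality effect rules out a person at 5/h or more.

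**Step 3. Is it corrected elsewhere?**

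- The central apnea index appears once in the whole document, in (q).
- The REI definition does not separate central from obstructive events, so the 5.0-14.9/h window cannot stand in for (q).
- The remaining eligibility checks listed in Section 8(b) are a pregnancy test, an oral exam and blood pressure. None concerns central events.
- Section 7 refers to a routine in-lab or home test, and Section 8(b) to three nights on a research monitor. Neither is named as the source of CAI.

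**Step 4. Could the sign be a PDF reading error?** In the same section the age criterion kept its greater-than-or-equal sign and (e) kept its less-than sign. An error in (q) alone is therefore unlikely, though not excluded. The source PDF would settle it.

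**Step 5. Size.** The documents give no distribution of CAI and no rule linking CAI to REI, so no percentage or count of affected people can be computed.

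**The case against.** The strongest reply is that any sleep clinician would see what was meant. The item excludes central sleep apnea, the number is only a parenthesis, and on a label-led reading a person with CAI 0 does not have the condition. Applied literally, (q) would turn away people with mild OSA and few or no central apneas, so staff would probably notice at once. Items (p) and (r) offer further protection, and no mis-enrolment is shown. This limits the likely harm. It does not repair the criterion, because a label-led reading works only by disregarding the printed threshold.

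Four narrower points also deserve credit:

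- An exclusion may narrow an inclusion, so (q) does not strictly contradict inclusion (c). The firm conflict is with its own label; inclusion (c) and the target population only show the intended direction.
- The eligibility checks in Section 8(b) are introduced as what assessment will include, so the list need not be complete. Section 10 shows that airflow and thoracic and abdominal movement are recorded, so signals relevant to event type are collected. The gap is that no section says how, or from which recording, CAI is obtained.
- A correctly read sign in (e) is only indirect evidence about the sign in (q). Item (g) prints a blood pressure with no comparison sign, which could come from the source or from extraction.
- Read literally, (b)-(d) also reverse, yet are treated here as minor. The difference is that (q) sets a numeric threshold that a form can apply mechanically, whereas (b)-(d) are phrasing slips with no figure in them.

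**Conclusion.** The concern holds. As written, (q) excludes CAI 0 and 4.9/h and does not exclude 5.0 or 10/h, which is the reverse of what its label says. The joint reading rescues the CAI 0 case but still fails at 5/h and above. The conclusion rests on the printed text being faithful to the source PDF.

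The practical effect is unquantified. With 40 participants planned and no CAI data in the documents, the number affected is unknown. Any effect would fall mainly on REI and related secondary outcomes. The primary outcome in Section 12 is days of device use out of 42, and nothing shows that its comparison between arms would be affected. This should be fixed because it is an eligibility threshold, not because harm has been demonstrated.

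**What to change.** 1. Reconcile the inequality in (q) with its label and with the target population, and confirm the boundary. The choice of limit is for the sponsor and investigator; none is proposed here.
2. State which recording supplies CAI: the routine diagnostic test or the three-night research monitor.
3. Check that the RedCap screening questionnaire and any eligibility form that records (q) use the same direction as the corrected text. Do the same for the records of anyone already enrolled.
4. In the same amendment, reword (b), (c) and (d) so that each names the condition that excludes.

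The cost is one corrected criterion, a short statement of the data source, three wording edits, and a check of the forms and of at most the 40 planned participants' records. The sample size and the analysis do not change.

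### Section 13 rests its safety provision on the approved indication although the trial randomises output, and no end-of-study summary of side effects by arm is planned

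*Combined protocol and SAP*

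**What the plan says.** Section 13 gives one sentence on safety analysis: "No interim analysis or interpretation of data for a safety signal are included as the eXciteOSA® therapy will be used for its approved indication". On collection and reporting it adds: "Any adverse event will be notable during the visit itself and any unexpected untoward event will be reported to the IRB by the PI", with a 48-hour limit.

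The contrast under study is set out in Section 10, Stimulation Level. At the top setting, "the maximum voltage (current) levels for the low and high intensity arms are 6.7 V (11.1 milliamps) and 29.8 V (58.6 milliamps), respectively". The delivered level is not fixed. Section 8 says: "Within each arm, the participant will be further able to further adjust the degree of stimulation level on a range of 1-15". Section 10 tells participants to move up as they tolerate it and lets them step down, even mid-session. It also says the device has FDA approval for snoring and mild sleep apnea, without linking that approval to either output.

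Section 15 has a single risk statement for both arms. It names three expected effects: "pooling of saliva, tooth sensitivity during use and tingling of the tongue that can continue after use". It gives no rates, and describes all of them as transient.

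The endpoints in the synopsis, Section 9 and Section 12 are adherence, REI, sleepiness, partner-rated snoring, quality of life, sleep quality, work productivity and acceptance of treatment. None is an adverse-event or tolerability outcome, and Section 12 describes no side-effect table. Section 6 gives 40 participants; the synopsis gives 20 per arm.

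**The concern.** The stated reason does not match the design. An argument from indication could support lighter monitoring if the arms differed in who was treated or for what. Here everyone has the same condition and the arms differ in electrical output. The reason therefore does not address the one thing that is randomised.

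This matters for reading the primary result. Section 4 puts the study question this way: "Foremost is the question of whether adherence is a function of the intensity of stimulation". Discomfort is a natural route from intensity to adherence, and because participants set their own level it also influences the exposure they receive. If adherence is lower in the high-intensity arm, the planned analyses could not say whether side effects were the reason. If adherence is similar, they could not say whether side effects were similar too, because participants may have turned the level down or put up with the effects.

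Acceptance of treatment is the closest listed outcome. It records whether a participant would take the treatment, not which side effects occurred or why use stopped.

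**Working it through.** **1. Size of the randomised contrast** (inputs from Section 10)

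- Maximum current: 58.6 / 11.1 = 5.28.
- Maximum voltage: 29.8 / 6.7 = 4.45.

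These are ratios of ceilings at setting 15. The delivered ratio is unknown because each participant chooses a level from 1 to 15.

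**2. The two readings of Section 13, set against Sections 9 and 12**

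| Reading of the sentence | What Section 13 excludes | What Sections 9 and 12 plan at study end |
|---|---|---|
| The word interim governs both analysis and interpretation | Review during the study only | No side-effect outcome, no by-arm summary |
| The word interim governs analysis only | Interim analysis, and any interpretation for a safety signal | No side-effect outcome, no by-arm summary |

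The last column is the same in both rows, so the gap does not depend on how the sentence is parsed.

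**3. Whether visit-based noting would fill the gap**

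Section 8 lists a consent visit with a 20-minute run-in, baseline assessments, and follow-up after six weeks. No visit is listed during the six weeks of home use. Section 15 says the listed effects resolve soon after use of the device stops. Effects that come and go at home are unlikely to be seen at the follow-up visit unless participants are asked. No side-effect form or question is described. A global assessment survey is in the baseline packet, which is repeated at follow-up, but its content is not given, so it cannot be counted either way.

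**4. What 20 per arm can show**

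The sample size of 40 comes with no alpha, power, effect size or standard deviation, so there is no figure of the plan's own to reproduce.

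If no events are seen in an arm of 20, the exact upper limits are:

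- one-sided 95%: 1 − 0.05^(1/20) = 0.139, or 13.9%;
- two-sided 95%: 1 − 0.025^(1/20) = 0.168, or 16.8%.

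The documents give no side-effect rates. The rates below are assumptions chosen to show a range (two-sided alpha 0.05, 20 per arm; the last column uses the normal approximation):

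| Low vs high arm | Power, normal approximation | Power, exact Fisher | Per arm for 80% power |
|---|---|---|---|
| 10% vs 30% | 0.35 | 0.24 | 62 |
| 20% vs 40% | 0.28 | 0.19 | 82 |
| 20% vs 50% | 0.51 | 0.41 | 39 |
| 10% vs 50% | 0.81 | 0.74 | 20 |

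Only a difference of about 40 percentage points from a low base comes close to reliable detection. That supports estimates with intervals and argues against a formal test.

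**The case against.** The strongest reply is that Section 13 is about monitoring during the study, so its sentence most naturally excludes interim review only. Adverse events are still to be noted at visits. The allocation table is released once the study is complete, so whatever is recorded could be tabulated by arm. Sending unexpected events to the IRB is a reporting rule and says nothing about what the final report will contain. Finally, Aim 1 asks whether adherence varies with stimulation level, not why.

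Much of this stands. A reader might infer that Section 13 bars all interpretation of safety data and that the trial therefore cannot show a difference in side effects. The documents do not support that: the wording allows the narrower reading, and nothing prevents a tabulation after unblinding. Nor may the five-fold figure be read as the contrast that participants actually receive. It is also true that no stated aim fails without a tolerability outcome.

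What the reply does not remove is the mismatch between the stated reason and the randomised factor, and the absence of any planned outcome, structured question or by-arm table. That a tabulation is possible afterwards is not a plan for one, and it is worth little if the transient effects of home use were never asked about.

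**Conclusion.** The point holds as an inexpensive improvement that should be made. Section 13 goes beyond silence: it gives an explicit rule, and its reason does not address a contrast with a 5.3-fold ratio in maximum current. On either reading of the sentence, the trial has no plan to show whether side effects differ by intensity.

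This conclusion rests on the listed endpoints and analyses being complete, and on the undefined global assessment survey not already recording side effects and reasons for stopping. If that survey does record them, only the by-arm table and the rationale need attention. Nothing here implies that either output is unsafe; the documents give no data on that. At 20 per arm the added result would be descriptive, not a basis for claiming equal tolerability.

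**What to change.** 1. **Section 13.** Replace the approved-indication rationale with one that applies to both randomised outputs, and state that only interim review is excluded.
2. **Sections 8 and 9.** Add a short structured question to the existing 6-week questionnaire packet. It should cover each of the three Section 15 side effects, and whether the participant stopped or interrupted use because of them. List side-effect-related stopping as a tolerability outcome.
3. **Section 12.** Pre-specify one descriptive end-of-study table by randomised arm: number and percent with each listed side effect, with any adverse event, and with side-effect-related stopping. Give exact 95% confidence intervals and no formal test.

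The cost is one added question, a few lines of text and one table. It needs no extra participants and no change to blinding or treatment. The drawback is imprecision, as the zero-event limits above show, and the text should say that the table is descriptive only.
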